## 12.5 Pregnancies

When an abnormality is reported in the foetus or newborn infant, information is needed from the male partner. Informed consent must be obtained prior to this.

Female subjects must be instructed to notify the investigator immediately if they become pregnant during the trial. The investigator must report any pregnancy in subjects who received Novo Nordisk provided trial product.

The investigator must report all information on pregnancies, including AEs in the subject, the foetus, and newborn infant on the trial related pregnancy forms. The pregnancy forms must be forwarded to Novo Nordisk preferably electronically in PDF format or by fax.

The investigator must follow the pregnancy until the pregnancy outcome and the newborn infant(s) until the age of one month. The investigator must collect information on the pregnancy and pregnancy complications as well as the pregnancy outcome including the health of the newborn infant(s) on the pregnancy forms.

The following must be collected:

- Initial information within 14 calendar days of the investigator's first knowledge of the pregnancy
- Information on the outcome of her pregnancy - including the health status of the newborn infant at the age of one month **within 14 calendar days of the investigator's knowledge of the pregnancy outcome**
- All non-serious AEs in connection with the pregnancy and pregnancy outcome must be reported on the pregnancy forms within 14 calendar days of the investigator's knowledge. It must be clear in the description if the event occurs in the subject, the foetus or the newborn infant.
- All SAEs in connection with the pregnancy and pregnancy outcome must be reported on the pregnancy forms following the **same timelines as required for other SAEs** (see section 12.2). It must be clear in the description if the event occurs in the subject foetus or the newborn infant.
  - The SAEs that must be reported include abnormal outcome - such as congenital anomalies, foetal death and termination of pregnancy (spontaneous or elective abortion), including any anomalies of the foetus observed at gross examination or during autopsy - as well as other pregnancy complications fulfilling the criteria of an SAE

## 12.6 Precautions and/or overdose

During treatment with insulin, there is a risk of hypoglycaemia (please refer to section [8.8](#)). Symptoms of hypoglycaemia usually occur suddenly and may include cold sweat, nervousness or tremor, anxious feelings, unusual tiredness, confusion, difficulty in concentrating, excessive hunger, temporary vision changes, headache, nausea and palpitation. Severe hypoglycaemia may lead to unconsciousness.

Hypoglycaemic episodes should be treated after best practise at the discretion of the investigator. In case of treatment with IDegAsp 30 attention should be given to the fact that the action profile of the basal component (IDeg) is flat and of somewhat longer duration than currently marketed long-acting insulin preparations. It may therefore take several hours more before stable normal blood glucose is achieved after a hypoglycaemic episode when compared to existing long-acting basal insulin analogues.

Symptoms of minor hypoglycaemia should be treated by ingestion of carbohydrate. Major hypoglycaemia resulting in loss of consciousness must be treated according to best medical practice (e.g. 25 ml of 50% dextrose solution given intravenously, or 0.5 - 1 mg of glucagon given subcutaneously or intramuscularly).

Please refer to the current edition of the IDegAsp 30 investigator's Brochure (IB). For BIAsp 30 please refer to the current version of the SPC or locally approved product information.

## **12.7 Committees related to safety**

### **12.7.1 Novo Nordisk safety committee**

Novo Nordisk will constitute an internal safety committee to perform ongoing safety surveillance. The safety committee may recommend unblinding of any data for further analysis, as the members of the safety committee are blinded to the treatment though this is an open-label trial. If so, an independent ad hoc group will be established to maintain the blinding.

### **12.7.2 Event adjudication committee**

An independent external clinical safety event adjudication committee (EAC) is constituted for this trial to perform ongoing adjudication of cardiovascular events.

The EAC is composed of permanent members covering required medical specialities. The EAC members must disclose any potential conflicts of interest and must be independent of Novo Nordisk. The EAC will have no authorisations to impact on trial conduct, trial protocol or amendments. The events are reviewed by the EAC in an independent and blinded manner. Adjudication will be completed based on a review of data collected from the sites. The provided data will be anonymised by identifiers.

An adjudication vendor will ensure that the EAC has access to the relevant medical source documentation required (for example X-ray, ECGs, ultrasound images, discharge summaries, pathology reports, and death certificates). The EAC will initiate the review and may ask for additional information that the investigator needs to provide if available.

Table 12–2 provides an overview of events subject for adjudication.

For AEs requiring adjudication, an adjudication form should also be completed in addition to the AE form.

**Table 12–2 Description of events to be adjudicated**

Type of event	Event description
Acute coronary syndrome	All types of myocardial infarction (MI): 

• Spontaneous MI (including re-infarction)

• MI secondary to ischemia due to imbalance between oxygen demand and supplies

• Percutaneous coronary intervention (PCI) related MI (including MI associated with stent thrombosis)

• Coronary artery bypass graft surgery related MI

• Silent MI

 Hospitalisation for unstable angina pectoris.  All events with symptoms of myocardial ischemia requiring hospitalisation
Cerebrovascular event	Any acute episode of focal or global neurological dysfunction caused by brain, spinal cord, or retinal vascular injury as a result of haemorrhage or infarction
Fatal event	All-cause death

Event adjudication will be performed for AEs in randomised subjects including AEs with an onset date during the screening period and including the 30 days follow-up period. Event adjudication will not be performed for AEs in screening failures

Events for adjudication can be captured by:

**1. Direct reporting by investigator**

For each AE reported in the eCRF, the investigator should tick the appropriate AE category on the AE form field to capture the relevant event for adjudication. The relevant forms will appear in the eCRF. For fatal events the death adjudication form is triggered from the outcome field on the AE form and will appear in the eCRF for the investigator to complete.

The investigator should complete the event specific form and the adjudication form within 14 days and upload source data preferably within 4 weeks.

## 2. Screening of AEs

All AEs will be screened to detect potential missed events for adjudication. If needed, the investigator will be asked to provide additional information such as an alternative aetiology.

Based on the information provided, the adjudication vendor or EAC will decide if the event is relevant for adjudication, although not initially reported as an event for adjudication by the investigator.

If so, an adjudication form will be triggered by Novo Nordisk in the eCRF and the investigator must provide source documentation preferably within 4 weeks of request.

## 3. EAC identified events

Potentially unreported events may be detected by the EAC in the provided source data. Site will be informed and asked to consider reporting. Regardless of reporting, the event will be adjudicated based on the source documents already provided.

For all events for adjudication, the investigator should provide the source documentation as soon as possible and on an ongoing basis. For further details regarding reporting please refer to the Event Adjudication Site manual.

Cardiovascular diseases are the leading cause of illness and death in subjects with diabetes. Concerns have been raised that some antidiabetic agents may impart greater cardiovascular risk than previously anticipated. DegAsp is not suspected to cause any greater risk of cardiovascular events than other insulin products and is not expected to create a higher risk compared to the risk in general for the diabetes population.

A list of International Statistical Classification of Diseases and Related Health Problems, 10th revision (ICD-10) codes representing examples of diagnoses that may be linked to ACS, stroke or cardiovascular death is provided below. The list is not complete, and additional diagnosis, signs and symptoms (e.g. cardiac enzyme changes and ECG findings) may be related to ACS, stroke or cardiovascular death, as evaluated by the investigator, and should thus also be reported.

### 12.7.2.1 Acute coronary syndrome

ACS covers the spectrum of clinical conditions ranging from unstable angina pectoris (UAP) to non ST elevation myocardial infarction (NSTEMI, in ICD -10 termed subendocardial or nontransmural) and ST elevation myocardial infarction (STEMI, in ICD -10 termed transmural).

#### **I20 Angina pectoris**

- I20.0 Unstable angina

#### **I21 Acute myocardial infarction**

- I21.0 Acute transmural myocardial infarction of anterior wall
- I21.1 Acute transmural myocardial infarction of inferior wall

- I21.2 Acute transmural myocardial infarction of other sites
- I21.3 Acute transmural myocardial infarction of unspecified site
- I21.4 Acute subendocardial myocardial infarction (nontransmural myocardial infarction (NOS))
- I21.9 Acute myocardial infarction, unspecified (myocardial infarction (acute) NOS)

**I22 Subsequent myocardial infarction** (Includes: recurrent myocardial infarction)

- I22.0 Subsequent myocardial infarction of anterior wall
- I22.1 Subsequent myocardial infarction of inferior wall
- I22.8 Subsequent myocardial infarction of other sites
- I22.9 Subsequent myocardial infarction of unspecified site

**I24 Other acute ischaemic heart diseases**

- I24.0 Coronary thrombosis not resulting in myocardial infarction
- I24.8 Other forms of acute ischaemic heart disease
  - Coronary failure
  - Coronary insufficiency
- I24.9 Acute ischaemic heart disease, unspecified

**12.7.2.2 Stroke**

Stroke is suspected if a new focal neurological deficit develops that is transient (but present more than 24 hr) or permanent.

**G46 Vascular syndromes of brain in cerebrovascular diseases**

- G46.3 Brain stem stroke syndrome
- G46.4 Cerebellar stroke syndrome
- G46.5 Pure motor lacunar syndrome
- G46.6 Pure sensory lacunar syndrome
- G46.7 Other lacunar syndromes
- G46.8 Other vascular syndromes of brain in cerebrovascular diseases

**I61 Intracerebral haemorrhage**

- I61.0 Intracerebral haemorrhage in hemisphere, subcortical
- I61.1 Intracerebral haemorrhage in hemisphere, cortical
- I61.2 Intracerebral haemorrhage in hemisphere, unspecified
- I61.3 Intracerebral haemorrhage in brain stem
- I61.4 Intracerebral haemorrhage in cerebellum
- I61.5 Intracerebral haemorrhage, intraventricular
- I61.6 Intracerebral haemorrhage, multiple localised
- I61.8 Other intracerebral haemorrhage
- I61.9 Intracerebral haemorrhage, unspecified

**I63 Cerebral infarction** (occlusion and stenosis of cerebral and precerebral arteries, resulting in cerebral infarction)

- I63.0 Cerebral infarction due to thrombosis of precerebral arteries
- I63.1 Cerebral infarction due to embolism of precerebral arteries
- I63.2 Cerebral infarction due to unspecified occlusion or stenosis of precerebral arteries
- I63.3 Cerebral infarction due to thrombosis of cerebral arteries
- I63.4 Cerebral infarction due to embolism of cerebral arteries
- I63.5 Cerebral infarction due to unspecified occlusion or stenosis of cerebral arteries
- I63.6 Cerebral infarction due to cerebral venous thrombosis, nonpyogenic
- I63.8 Other cerebral infarction
- I63.9 Cerebral infarction, unspecified

**I64 Stroke, not specified as haemorrhage or infarction** (Cerebrovascular accident NOS)

#### **12.7.2.3 Cardiovascular death**

Sudden, unexpected cardiac death involving cardiac arrest or sudden unexpected vascular death.

#### **I 46 Cardiac arrest**

- I46.1 Sudden cardiac death
- I46.9 Cardiac arrest, unspecified

#### **R96 Other sudden death, cause unknown**

- R96.0 Instantaneous death
- R96.1 Death occurring less than 24 hours from onset of symptoms, not otherwise explained

#### **R98 Unattended death**

- R99 Other ill-defined and unspecified causes

## 13 Case report forms

For this trial a combination of eCRF and paper CRF will be used.

Novo Nordisk will provide a system for the eCRFs. This system and support services to the system will be supplied by a vendor.

The investigator must ensure that all relevant questions are answered, and that no empty data fields exist. If a test or an assessment has not been done and will not be available, or if the question is irrelevant (e.g. is not applicable), indicate this according to the data entry instructions.

The investigator must ensure that all information is consistent with the source documentation. By electronically signing the case book, the investigator confirms that the information in the eCRF and included related forms are complete and correct.

The following will be provided as paper CRFs only:

- Pregnancy forms
- PRO questionnaires

In addition, paper safety information forms, AE forms and technical complaint forms will be provided. These must be used when technical issues prevent access to the eCRF or access to the eCRF is revoked.

On the paper forms, print legibly, using a ballpoint pen. Ensure that all questions are answered, and that no empty data blocks exist. Ensure that no information is recorded outside the data blocks. If a test/assessment has not been done and will not be available, indicate this by writing “ND” (not done) in the appropriate answer field in the CRF. If the question is irrelevant (e.g. is not applicable) indicate this by writing “NA” (not applicable) in the appropriate answer field. Further guidance can be obtained from the instructions in the CRF.

### 13.1 Corrections to case report forms

Corrections to the eCRF data may be made by the investigator or the investigator’s authorised staff. An audit trail will be maintained in the CRF application containing as a minimum: the old and the new data, identification of the person entering the data, date and time of the entry and reason for the correction. If corrections are made by the investigator’s authorised staff after the date the investigator has signed the case book, the case book must be signed and dated again by the investigator.

Corrections to the data in the paper CRFs may only be made by drawing a straight line through the incorrect data and then writing the correct entry next to the data that were crossed out. Each correction must be initialled, dated and explained (if necessary) by the investigator or the

investigator's authorised staff. If corrections are made by the investigator's authorised staff after the date of the investigator's signature on the electronic signed case book, the case book must be signed again, electronically, by the investigator. Corrections necessary after the CRFs have been removed from the investigator's site must be documented on a data clarification form (DCF) or a monitor-initiated discrepancy form (MIDF). If the case book for the subject has not yet been electronically signed, any corrections must be approved by the investigator or her/his authorised staff. If the case book for the subject has already been signed, the investigator must approve any correction.

### **13.2 Case report form flow**

The investigator must ensure that data are recorded in the eCRF as soon as possible after the visit/phone contact, preferable within 5 calendar days. During the trial, SMPG measurements and corresponding insulin doses for titration purpose should be recorded within 24 hours after the visit/phone contact. At the end of the trial the investigator must ensure that all remaining data have been recorded in the eCRF no later than 24 hours after last subject's last visit at the site. Once data have been entered, they will be available to Novo Nordisk for data verification and validation purposes.

Site specific eCRF data (in an electronic readable format) will be provided to the site before access to the eCRF is revoked. These data must be retained at the site.

## 14 Monitoring procedures

During the course of the trial, the monitor will visit the trial site to ensure that the protocol is adhered to, that all issues have been recorded, to perform source data verification and to monitor drug accountability. The first monitoring visit will be performed as soon as possible after FPFV and no later than 4 weeks after. The monitoring visit intervals will depend on the outcome of the remote monitoring of the eCRFs, the trial site's recruitment rate and the compliance of the trial site to the protocol and GCP, but will not exceed 12 weeks.

The monitor must be given direct access to source documents (original documents, data and records). Direct access includes permission to examine, analyse, verify and reproduce any record(s) and report(s) that are important to the evaluation of the trial. If the electronic medical record does not have a visible audit trail, the investigator must provide the monitor with signed and dated printouts. In addition the relevant trial site staff should be available for discussions at monitoring visits and between monitoring visits (e.g. by telephone).

The monitor will collect CRF pages and other trial related forms containing data from screening failures. Data on the safety information form needs to be source data verified.

All data must be verifiable in source documentation other than the CRF.

There must be a source document agreement at each site. There should only be one source defined at any time for any data element.

Monitors must review the medical records and other source data (e.g. the diaries and PROs) to ensure consistency and/or identify omissions compared to the eCRF. If discrepancies are found, the investigator must be questioned about these. Diaries and 2nd copy (third page) of the PROs must not be removed from site.

## 15 Data management

Data management is always the responsibility of Novo Nordisk.

Appropriate measures, including encryption of data files containing person identifiable data, will be used to ensure confidentiality of subject data, when they are transmitted over open networks.

Laboratory data from central laboratories will be transferred electronically from the laboratory performing the analyses. In cases where laboratory data are transferred via non-secure electronic networks, data will be encrypted during transfer.

The subject and any biological material obtained from the subject will be identified by subject ID and trial identification number. Appropriate measures such as encryption or leaving out certain identifiers will be enforced to protect the identity of subjects in all presentations and publications as required by local, regional and national requirements.

## 16 Computerised systems

Novo Nordisk will capture and process clinical data using computerised systems that are described in Novo Nordisk Standard Operating Procedures (SOPs) and IT architecture documentation. The use and control of these systems are documented.

Investigators working on the trial may use their own electronic systems to capture source data. Novo Nordisk will collect information on the practical use of these systems within the conduct of this clinical trial.

## 17 Statistical considerations

Novo Nordisk will analyse and report data from all sites together.

Analyses of all endpoints will be based on the Full Analysis Set (FAS). The primary efficacy analysis will be repeated on the Per Protocol (PP) analysis set in accordance with the Committee for Proprietary Medicinal Products (CPMP) Points to Consider.

Secondary confirmatory and supportive efficacy endpoints and patient reported outcome endpoints will be summarised using the FAS. Safety endpoints will be summarised using the Safety Analysis Set (SAS).

The impact of protocol deviations and outliers may be investigated further in sensitivity analyses if deemed relevant.

The primary objective of this trial is to confirm efficacy of the investigational product in terms of glycaemic control as assessed by HbA1c. If efficacy of the investigational product can be confirmed as assessed by comparing the mean HbA1c treatment difference to a non-inferiority limit of 0.4%, the trial also aims to show superiority of the investigational product over the comparator for a number of confirmatory secondary endpoints. The family-wise type I error rate will be controlled in the strong sense using a hierarchical (fixed sequence) testing procedure. This is based on a priori ordering of the null-hypotheses and testing them in this order using the two-sided 95% confidence interval approach until an insignificant result appears. The effect is that superiority only will be confirmed for endpoints where all previous null-hypotheses have been rejected.

In addition, if non-inferiority can be confirmed and the 95% confidence interval for the mean HbA1c treatment difference not only lies entirely below 0.4% but also below zero this will be considered as evidence of superiority of the investigational product over the comparator in terms of change from baseline in HbA1c after 26 weeks of treatment.

Only endpoints derived after 26 weeks of treatment will be analysed statistically. Missing values will be imputed using the Last Observation Carried Forward (LOCF) method. LOCF has been a standard approach in diabetes trials for many years, and was used as the primary analysis in all degludec phase 3a trials. LOCF is considered to be an appropriate method in the context of treat-to-target trials, where subjects after withdrawal typically continue their therapy using commercially available insulin. In previous treat-to-target trials with degludec LOCF has generally provided similar results to alternative methods to handle missing data, such as repeated measures models and completer analyses. In this trial, similar sensitivity analyses will be made to examine the robustness of the LOCF method. All endpoints will be summarised descriptively at each visit by treatment and in total using observed data. After 26 weeks of treatment, descriptive statistics will be presented based both on observed and LOCF imputed data. Endpoints that are analysed untransformed and

endpoints that are not formally analysed are summarised by the arithmetic mean, standard deviation (SD), median, and minimum and maximum value. Endpoints that are analysed log-transformed are summarised by the geometric mean, CV, median, minimum and maximum value.

LOCF imputed data will be used as the basis for plotting data if not otherwise specified.

Presentation of results from a statistical analysis will include the estimated mean treatment effects (least-squares means [LSMeans]) for absolute values and change from baseline if applicable. Estimated mean treatment differences (or ratios) will be presented together with two-sided 95% confidence intervals for all endpoints analysed statistically. p-values will only be presented for the primary and the confirmatory secondary endpoints for which formal statistical testing will be performed. The other endpoints are considered supportive and explorative in nature and no p-values will be presented.

For endpoints measured over time mean values will be plotted to explore the trajectory over time. For survival endpoints, Kaplan-Meier plots are presented for each treatment. Data collected before randomisation will only be summarised descriptively.

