## 4 Objectives and endpoints

### 4.1 Objectives

#### 4.1.1 Primary

To confirm the efficacy of IDegAsp 30 BID  $\pm$  metformin in controlling glycaemia with respect to change from baseline in HbA1c after 26 weeks of treatment. This is done by comparing the difference in change from baseline in HbA1c after 26 weeks of treatment between IDegAsp 30 and BIAsp 30 both BID  $\pm$  metformin, to a non-inferiority limit of 0.4%, and if non-inferiority is confirmed, to a superiority limit of 0%.

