### 17.1 Sample size calculation

The primary objective of this trial is to confirm efficacy of IDegAsp 30 BID ± metformin in terms of glycaemic control.

This is done by showing that:

IDegAsp 30 BID ± metformin is non-inferior to BIAsp 30 BID ± metformin in terms of glucose lowering effect as assessed by change from baseline in HbA1c after 26 weeks of treatment using a non-inferiority margin of 0.4% (absolute). Sample size is determined based on this primary objective.

Throughout this section of the protocol the term “investigational product” will be used as a synonym for IDegAsp 30 and the term “comparator” will be used as a synonym for BIAsp 30 BID.

The non-inferiority margin of 0.4% (absolute) was chosen in accordance with the FDA guidance. Let D be the mean treatment difference for change in HbA1c (investigational product minus comparator). The null-hypothesis will be tested against the alternative hypothesis of non-inferiority as given by

$H_0: D > 0.4\%$  against  $H_A: D \leq 0.4\%$

Operationally the null-hypothesis will be rejected and non-inferiority considered confirmed if the upper bound of the two-sided 95% confidence interval for the mean HbA1c treatment difference is below or equal to 0.4%. This is equivalent to using a one-sided test of size 2.5%.

Sample size is determined using a t-statistic under the assumption of a one-sided test of size 2.5% and a zero mean treatment difference (i.e. D=0%). Based on experience from previous phase 3 trials in subjects with type 2 diabetes treated with insulin an estimate for the standard deviation (SD) of 1.3% for HbA1c will be used in the sample size calculation ([Table 17-1](#)). The sample size calculation is done using SAS 9.3.

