#### Statistical analysis

Change from baseline in HbA1c after 26 weeks of treatments will be analysed using an Analysis of Variance (ANOVA) method with treatment, anti-diabetic therapy at screening and sex as fixed factors, and age and baseline HbA1c as covariates. The anti-diabetic therapy at screening is a factor with the following four levels:

1. Basal insulin regimen without metformin
2. Basal insulin regimen with metformin
3. Premix/self-mix regimen without metformin
4. Premix/self-mix regimen with metformin

The model will be fitted to all the data simultaneously (all treatment groups) and from this model the relevant treatment differences will be estimated.

Non-inferiority will be considered confirmed if the upper bound of the two-sided 95% confidence interval is below or equal to 0.4% or equivalent if the p-value for the one-sided test of

$H_0: D > 0.4\%$  against  $H_A: D \leq 0.4\%$ ,

is less than or equal to 2.5%, where D is the mean treatment difference (investigational product minus comparator)

If non-inferiority is confirmed the superiority of the investigational product over comparator will be investigated. Superiority will be considered confirmed if the upper bound of the two-sided 95% confidence interval, which is calculated using the FAS, is below 0%. The PP analysis is considered supportive here.

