## **17.4 Secondary endpoints**

### **17.4.1 Confirmatory secondary endpoints**

Provided that non-inferiority is confirmed for the primary endpoint, a number of confirmatory secondary endpoints will be tested to confirm superiority of the investigational product over the comparator.

The confirmatory secondary endpoints are given below together with the direction of the test for superiority. The order of the endpoints defines the testing sequence.

1. Change from baseline in FPG after 26 weeks of treatment (analysed at central laboratory)
  - Superiority is considered confirmed if the 95% confidence interval for the treatment difference (investigational product minus comparator) is entirely below zero
2. Number of treatment emergent nocturnal confirmed hypoglycaemic episodes
  - Superiority is considered confirmed if the 95% confidence interval for the relative risk (investigational product / comparator) is entirely below one
3. Number of treatment emergent confirmed hypoglycaemic episodes
  - Superiority is considered confirmed if the 95% confidence interval for the relative risk (investigational product / comparator) is entirely below one
4. Change from baseline in body weight after 26 weeks of treatment
  - Superiority is considered confirmed if the 95% confidence interval for the treatment difference (investigational product minus comparator) is entirely below zero
5. Responder without hypoglycaemic episodes (HbA1c <7.0% after 26 weeks of treatment and no confirmed episodes during the last 12 weeks of treatment or within 7 days after the last randomised treatment including only subjects exposed for at least 12 weeks)
  - Superiority is considered confirmed if the 95% confidence interval for the odds ratio (investigational product / comparator) is entirely above one

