2.3.1 Statistical analysis

Change from baseline in HbA_{1c} after 26 weeks of treatments will be analysed using an Analysis of Variance (ANOVA) method with treatment, anti-diabetic therapy at screening and sex as fixed factors, and age and baseline HbA_{1c} as covariates. The anti-diabetic therapy at screening is a factor with the following four levels:

- Basal insulin regimen without metformin
- Basal insulin regimen with metformin
- Premix/self-mix regimen without metformin

- Premix/self-mix regimen with metformin

The model will be fitted using FAS and from this model the relevant treatment differences will be estimated.

Non-inferiority will be considered confirmed if the upper bound of the two-sided 95% confidence interval is below or equal to 0.4% or equivalent if the p-value for the one-sided test of

$H_0: D > 0.4\%$ against $H_A: D \leq 0.4\%$,

is less than or equal to 2.5%, where D is the mean treatment difference (investigational product minus comparator)

If non-inferiority is confirmed the superiority of the investigational product over comparator in change from baseline HbA_{1c} (%) after 26 weeks of treatment will be investigated. Superiority will be considered confirmed if the upper bound of the two-sided 95% confidence interval, which is calculated using the FAS, is below 0%. The PP analysis is considered supportive here.

The HbA_{1c} analyses will be carried out in both standard unit (%) and converted unit (mmol/mol), but the results given in % are considered confirmatory. Subjects with HbA_{1c} < 4.1 % (i.e. LLOQ) will get a converted value of LLOQ/2=10.6565 mmol/mol instead of the negative value that would have resulted from using the standard formula $10.93 * \text{value}(\%) - 23.5$.

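### HbA1c superiority is tested at full alpha outside the fixed sequence, so the promised strong family-wise error control fails and the error can almost double

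*Protocol*

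**What the plan says.** Protocol section 17, repeated in SAP section 2, states: "The family-wise type I error rate will be controlled in the strong sense using a hierarchical (fixed sequence) testing procedure". The mechanism is to order the null hypotheses in advance and go on "testing them in this order using the two-sided 95% confidence interval approach until an insignificant result appears".

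The order is in Protocol 17.4.1 and SAP 2.4.1: FPG, nocturnal confirmed hypoglycaemia, all confirmed hypoglycaemia, body weight, and responder without hypoglycaemia. The condition for starting it is HbA1c non-inferiority alone: "Provided that non-inferiority is confirmed for the primary endpoint, a number of confirmatory secondary endpoints will be tested to confirm superiority". HbA1c superiority is not on the list.

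HbA1c superiority is provided for elsewhere:

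- Protocol 4.1.1, as part of the primary objective: "and if non-inferiority is confirmed, to a superiority limit of 0" per cent.
- Protocol 17, in a separate paragraph after the description of the sequence: "this will be considered as evidence of superiority of the investigational product over the comparator in terms of change from baseline" in HbA1c.
- Protocol 17.3: "Superiority will be considered confirmed if the upper bound of the two-sided 95% confidence interval, which is calculated using the FAS, is below 0" per cent. SAP 2.3.1 has the same rule, introduced by "If non-inferiority is confirmed the superiority of the investigational product over comparator in change from baseline" in HbA1c.

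Neither document divides alpha between this test and the secondary list, or says which comes first.

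**The concern.** Testing superiority after non-inferiority on the same HbA1c interval costs no alpha, because the two hypotheses are nested. That argument covers one endpoint. It does not cover a second family of superiority tests that starts from the same non-inferiority gate at the same full level.

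As written, non-inferiority opens two branches: (a) HbA1c superiority and (b) the five-step list. Each runs at 2.5% one-sided whatever happens in the other. If the HbA1c superiority null and a secondary null that can be reached are both true, there are two separate chances of a false superiority claim.

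This situation is realistic. Protocol section 3 describes an earlier trial in an Asian population with comparable HbA1c, significantly lower FPG, a non-significant 33% reduction in nocturnal hypoglycaemia and a similar 24-hour rate. Under that pattern the FPG step is passed, and a hypoglycaemia null may be true together with the HbA1c superiority null. The trial is meant for registration in China, so a false confirmatory claim would matter.

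**Working it through.** **1. Can one order satisfy the text?** If HbA1c superiority came before FPG, its failure would stop the list. That contradicts 17.4.1, which asks only for non-inferiority. If it came after the responder endpoint, 17.3 would be wrong, because it tests superiority directly after non-inferiority. No single order fits both sections, so the procedure branches.

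**2. The plan's own figures.** The documents give no numerical family-wise error. Their planning inputs (Protocol 17.1) are margin 0.4%, SD 1.3%, true difference 0, 2.5% one-sided and allocation 2:1. A noncentral t calculation gives 87.1% power at 304/152, hence 456, and reproduces all 16 cells of Table 17-2. Then 456/0.85 = 536.5, which rounds up to 537 for an exact 2:1 split (358/179). The sample size is reproduced.

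**3. Error if non-inferiority is certain.** With both nulls true and independent:

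1 - (1 - 0.025)² = 1 - 0.9506 = 4.94%. The Bonferroni ceiling is 0.025 + 0.025 = 5.0%.

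**4. Error with the non-inferiority gate.** Let Z1 be the HbA1c statistic and Z2 the statistic of the first reachable secondary endpoint, both signed in favour of IDegAsp 30, and let δ = 0.4/SE. HbA1c superiority implies non-inferiority, so

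FWER = 0.025 + P(1.96 - δ < Z1 ≤ 1.96 and Z2 > 1.96).

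At 358/179:

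- SE = 1.3 × √(1/358 + 1/179) = 0.119
- δ = 0.4/0.119 = 3.36
- P(non-inferiority) = Φ(3.36 - 1.96) = 0.919
- Under independence, FWER = 0.025 + 0.025 × (0.919 - 0.025) = 4.74%, or 1.89 times nominal.

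At 304/152, the same steps give P(non-inferiority) = 0.872 and FWER = 0.025 + 0.025 × (0.872 - 0.025) = 4.62%, or 1.85 times.

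**5. Effect of correlation.** The documents give no correlation between endpoints, so this is an assumed range. It uses the bivariate normal, SD 1.3% and true HbA1c difference 0.

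| Correlation | Gate certain | Gated, 358/179 | Gated, 304/152 |
|---|---|---|---|
| -0.3 | 4.99% | 4.41% | 4.18% |
| 0 | 4.94% | 4.74% | 4.62% |
| 0.3 | 4.76% | 4.73% | 4.69% |
| 0.5 | 4.54% | 4.53% | 4.53% |
| 0.7 | 4.17% | 4.17% | 4.17% |
| 0.9 | 3.52% | 3.52% | 3.52% |

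With an assumed SD of 1.0% at 358/179, simulation gives 4.91%, 4.90% and 4.56% at correlations -0.3, 0 and 0.5. Every case exceeds 2.5%.

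**6. FPG truly lower, nocturnal hypoglycaemia null.** The second branch reaches its true null only if the FPG test succeeds, so its 2.5% is multiplied by the FPG power, which the documents do not give. With independence and a certain gate, FWER = 1 - 0.975 × (1 - 0.025 × power). That is 3.7%, 4.2% and 4.7% for assumed FPG power of 50%, 70% and 90%, and it approaches 4.94% as the power approaches 1.

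**7. After repair.** Simulation at 358/179 with all superiority nulls true, at correlations 0, 0.3 and 0.5, gives 2.5% if HbA1c superiority stands first in a single sequence and 2.3% to 2.5% if it stands last.

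**The case against.** The best defence is that the strong-control sentence sits in the paragraph about non-inferiority and the confirmatory secondary endpoints. For that family, non-inferiority followed by five ordered tests, control does hold at 2.5% one-sided. HbA1c superiority comes in the next paragraph as an addition, so the promise might be read as not covering it. HbA1c superiority taken alone also stays at 2.5%; only the union of the two branches is inflated.

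This reading does not survive the rest of the text. HbA1c superiority is in the stated primary objective. Protocol 17.3 calls it confirmed, the same term used for the five secondary tests. SAP 2.3.1 treats the HbA1c results in per cent as confirmatory, and in this connection only the PP analysis is called supportive.

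Two further objections concern size and stand in part. The inflation depends on a correlation that the documents do not give, and strong positive correlation reduces it. When FPG is truly lower, limited FPG power also reduces it. Both lower the error in particular cases. Neither rescues strong control, which must hold under every configuration of true and false nulls.

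**Conclusion.** The concern holds. The statement of strong family-wise control is not true of the procedure described. With HbA1c superiority and the first reachable secondary null both true, the one-sided error is about 1.8 to 1.9 times the nominal 2.5% for correlations from 0 to 0.5, and 1.4 times at 0.9. It cannot exceed 5.0%. The figures rest on normal test statistics, a true HbA1c difference of 0, the planning SD of 1.3% and the assumed correlations.

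The non-inferiority conclusion, the sample size of 456/537 and error control within the five-step list are not affected. The correction is still needed, because both documents make an explicit claim that the design does not meet, and the order has to be fixed before results are known.

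**What to change.** Either of two changes restores control:

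- **Number HbA1c superiority in the single sequence.** For example: HbA1c non-inferiority, then the five secondary endpoints as listed, then HbA1c superiority as step 6. The non-inferiority test, the sample size and the five secondary tests keep their present level and power. The price is that HbA1c superiority is reached only if all five earlier tests succeed. Under the pattern of the earlier Asian trial the sequence would stop at nocturnal hypoglycaemia. Placing it before FPG also controls the error, but then the secondary list would depend on HbA1c superiority.
- **Declare HbA1c superiority supportive**, with no confirmatory claim. This costs no power, but the primary objective must be reworded.

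A third possibility is to split the 2.5% between the two branches, at the cost of power in both.

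The chosen rule should be written identically in the Protocol (Summary, 4.1.1, 17, 17.3 and the list in 17.4.1) and the SAP (2, 2.3.1 and the list in 2.4.1). No extra subjects or data are needed.
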